During exercise at Duquesne, participants will be monitored for signs associated with a cardiac event based on the American College of Sports Medicine (ACSM) *Indications for Terminating Exercise Testing* protocol. These indications include: onset of angina, signs of poor perfusion (dizziness, confusion, light-headedness, ataxia), failure of heart rate to rise with exercise, severe fatigue, or subject request to stop. To determine if any of these indications occur, participants will be visually monitored and heart rate will be displayed in real-time at Duquesne trials. All participants will be notified that they may stop exercising if they feel short of breath, chest pain, abnormal back pain, or extremely fatigued. Also, patients are instructed that if they feel that their exertion reaches a 17 on the Borg Scale, they can stop walking. All research staff will be trained on this protocol and medical emergency management associated with a medical event. An emergency action plan will be stored in the laboratory and will be reviewed quarterly. [name], MD will serve as our medical PI on this study. Any adverse reaction will be evaluated by [name] within 1 week of the event. “At home” trials will be additionally monitored through an online diary using Qualtrics Survey Platform, which allows the patient to record adverse events for the PIs. Qualtrics is supported by both Duquesne University and the University of Pittsburgh for research using surveys. Qualtrics servers are protected by high-end firewall systems and use Transport Layer Security encryption for all transmitted data. For ‘at home’ trials, subjects cannot be monitored for signs associated with a cardiac event, however, subjects will be made fully aware of these signs and told to stop exercising if they experience any of these symptoms. Subjects will be instructed to contact [name] or [name] via a Google Voice number immediately when these symptoms occur. If these symptoms do not resolve within 15 minutes of resting, subjects will be instructed to seek medical help. Any adverse events will be discussed immediately (subjects will have [name], [name] and [name] contact information) and during the single trial that occurs each week at Duquesne. To ensure [name] or [name] is available to take these phone calls, a Google Voice number will be set up. This is the phone number subjects will be given. Calling this number will route the call to any of [name] or [name] existing phone numbers while maintaining privacy of personal contact information.

Risk of injury related to cutaneous mechanical testing is extremely rare and unlikely⁴. Mechanical testing is widely used and safe. Risks to the individual are minimal, because 1) subjects are instructed that they may stop any procedure at any time with no adverse consequences; and 2) the level of sensation experienced by subjects is at or below their tolerance level and threshold for pain.

Risk of injury related to thermal pain testing is minimal⁴. Thermal testing is widely used and safe. While thermal testing does produce pain, risks to the individual are minimal, because 1) the pain is transient in nature and generally subsides immediately after the procedure; 2) subjects are instructed that they may stop any procedure at any time with no adverse consequences; and 3) the level of pain experienced by subjects is below their tolerance level. With thermal stimulation there is a very slight risk of a burn, but this is minimized by the following: 1) positive lockout of stimulus parameters above 50°C; 2) the stimulator has built in a shut-down system to prevent the delivery of prolonged or high intensity stimuli (20 sec); 3) and before each use, temperature at probe will be verified with an electronic thermometer. Trials will proceed only if temperature detected at 20 sec cutoff is $\leq 50^{\circ}\text{C}$. Colleagues who have used this pain paradigm inform us that they have completed thermal testing with this stimulator on over 1000 subjects without producing a single burn. However, skin will be monitored for changes consistent with burns, such as redness that persists greater than one day and blistering. If a burn occurs, standard medical treatment will be recommended.

Risk of injury related to pressure pain testing is minimal^{4,7}. Pressure testing is widely used and safe. While pressure testing does produce pain, risks to the individual are minimal, because 1) the pain is transient in nature and generally subsides immediately after the procedure; 2) subjects are instructed that they may stop any procedure at any time with no adverse consequences; 3) the level of pain experienced by subjects is below their tolerance level; and 4) the pain applied is never more than that subjects pain threshold, which is well below any pressure that could cause damage.

Participants will be made aware during the consent process that they may withdraw from participation at any time during their enrollment.

URLS TO GUIDED MEDITATION RECORDINGS

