During the enrollment period, subjects will also be given a full description of all sensory and pain measures that will be taken. With initial consent, all subjects will be allowed to experience all sensory/pain measures before baseline pain testing is completed. All sensory and pain assays are based on well-established assays used in both healthy human participants and patients with chronic pain^{4,5}. All assays involve either innocuous (non-painful stimuli) or acute noxious stimuli (painful stimuli) that do not damage tissue. Sensory testing will be completed on both the non-dominant forearm and low back. For testing completed on the forearm, subjects will be seated in a chair with their arm supported. For testing completed on the low back, subjects will be positioned in prone on a plinth table with a head rest. Time between different tests will be >5 min to allow the subject to rest. Order of the three stimuli (e.g. mechanical, thermal, pressure) will be randomized during each day 1 versus day 29 testing. Training and description of each measure is as follows:

Cutaneous mechanical sensitivity assay⁴: Assay involves determining the sensitivity threshold for innocuous cutaneous stimulation and noxious cutaneous stimulation. Stimulation is provided with standard sensory evaluator filaments. These small nylon filaments each apply a single force (ranging from 0.008g to 4g). Before the start of the first experimental trial (baseline testing), subjects will be allowed to feel and manipulate the filaments. Starting with the smallest filament (0.008g; typically below the sensory threshold for human detection), 5 trials will be directed at the subject’s forearm and low back. Experimenter will ask “Can you feel

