Heat sensitivity assay⁴: Assay involves determining the sensitivity threshold for painful thermal stimulation. Stimulation is provided with a small thermal device, which will be strapped to the subject’s forearm then lower back at the site of back pain (Medoc Instruments). Before the start of the training/ experimental trials, subjects will be shown the device and allowed to feel the stimulus with their hand. Subjects are told to press the ‘stop’ button on a remote and/or verbally tell the experimenter to stop testing when they feel the stimulus transition from “innocuous warmth or heat” to “painful heat.” Each trial lasts for a maximum of 20 sec. The device is set so that typical withdrawal thresholds occur at approximately 10 seconds into the trial. The temperature on the probe tip at this point is $\sim 47^{\circ}\text{C}$ (116°F). The maximum temperature of the trial at the 20 second cutoff time point is 50°C (120°F). Temperatures in US desert areas often reach this temperature and research has shown that testing of the skin at this temperature for this length of time does not produce skin damage⁶. Additionally, this testing modality has been safely used a part of a standard pain/sensory testing protocol⁵. Total testing time is < 5 min.

A second assay will be used to evaluate the quality and unpleasantness of thermal pain. Each subject will receive a constant 45°C stimulus. 45°C is a standard temperature that is the typical minimal stimulus necessary to feel thermal pain. Stimulus (3cm x5cm heating block) will be applied for 3 seconds. Immediately following stimulus, the subject will be asked to evaluate the quality and unpleasantness of the pain. This is done with a standard 0-10 visual analog scale (VAS). On the “quality scale”, “0” is represented as “no pain” and “10” is represented as “the worst pain imaginable.” On the “unpleasantness scale”, “0” is represented as “not unpleasant” and “10” is represented as “the most unpleasant sensation imaginable.”

Example instructions for quality VAS – *“Please use the scale below to tell us how intense your pain is. Place an “X” on the scale that best describes the intensity of your pain.”*

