Mechanical pressure sensitivity assays⁷: Assay involves determining the sensitivity threshold for painful pressure stimulation and then determining the quality and unpleasantness of that same pressure in a separate trial. Stimulation is provided with a standard clinical pressure algometer (see below “instrument” section). This device consists of a probe connected to a pressure meter. The probe is placed on the subject’s forearm and low back at the site of back pain and pressure is gradually applied. Before the first training/experimental trial subjects will be allowed to apply the stimulus to themselves. During a trial, pressure will gradually be applied until the stimulus transitions from “innocuous pressure” to “painful pressure.” At this point, subject will say “stop” and the stimulus will be removed from the subject’s lower back. When algometer is removed from the subject, the greatest pressure applied is automatically recorded in the device. This is the “pressure pain threshold” for the trial. 2 trials will be applied to each the forearm and low back in two distinct sites at least 1 inch from each other to avoid damage or sensitization to a single area. After the pressure threshold has been determined for a subject, 1 additional trial will be applied (in a third testing site). In this trial, the subject will be asked to evaluate the quality and unpleasantness of a pressure stimulus given for 3 seconds. This is done with a standard 0-10 visual analog scale (VAS). On the “quality scale”, “0” is represented as “no pain” and “10” is represented as “the worst pain imaginable.” On the “unpleasantness scale”, “0” is represented as “not unpleasant” and “10” is represented as “the most unpleasant sensation imaginable.” During this trial, the experimenter will tell the subject that they are going to apply a painful stimulus to the subject and then ask the subject to evaluate that pain (on the two VASs). The exact stimulus will be matched to the subject’s pain threshold determined during the baseline trials

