(e.g. if baseline trials indicated a pressure threshold of 50 N then subject will be asked to evaluate the pain of that stimulus). During final testing trial (day 29), the pressure pain threshold will be re-measured to determine if there is a change from baseline. For the quality/unpleasantness testing, subjects will be tested on day 29 at their original baseline pressure threshold (from day 1) AND the new threshold determined day 29. This will allow an analysis of change from baseline and pain at threshold across the experiment.

Following baseline pain testing, subjects (in the exercise only and meditation then exercise groups) will be set-up for training on the exercise protocol. Subjects will become familiarized with the exercise protocol, including the physiological measures to be assessed [heart rate (HR)], the Borg Rate of Perceived Exertion (RPE) Scale, and the treadmill speed at which they will be walking. Subjects will be instructed to step up onto the treadmill and stand on the sides not the belt or belt deck. The researcher will slowly raise the speed to 2 mph. The subject will be instructed to step on the treadmill at this time. After 30 seconds, the speed will be ramped up to 2.5 mph and after another 30 seconds, the speed will be ramped up to their prescribed session speed (± 3.5 mph). They will also be instructed to walk with a natural gait pattern, allowing bilateral arm swing. To allow a natural arm swing, subjects are unable to hold onto the treadmill arm rails. Subjects will be introduced to the Borg RPE scale and asked to provide subjective feedback on their level of exertion at the initiation of and during the final minute of this 5 minute training period (Borg).

Intervention Sessions

Subjects will be scheduled for 20 intervention sessions during their time in the study – that is five sessions per week over four weeks. Subjects are only required to return to campus for the first session of each week. The remaining four weekly sessions can be completed at home on a personal treadmill or in the community, such as a local gym. Subjects are able to complete all sessions at Duquesne University if that is their preference. Sessions will be scheduled/encouraged to occur at the same approximate time each day to control for factors that may influence exercise performance and assessments.

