Title Page:

Statistical Analysis Plan

Combined exercise and meditation as a treatment for patients with chronic back pain

NCT number not available

12/21/17

Statistical Analysis Plan
Combined exercise and meditation as a treatment for patients with chronic back pain

This is a single-blind, single center randomized clinical trial comparing a treatment group (MedExT) versus a control group. The current analysis plan is specific to this study for reporting and publication purposes but is part of a larger study. The primary outcome of this study is to compare the post Roland-Morris Disability Questionnaire scores between the two independent groups. This will be achieved by comparing the mean post disability score for the MedExT group to the mean post disability score for the control group using a two-sample t-test (or the Mann-Whitney-Wilcoxon rank sum test if normality does not hold) in which a one-sided p-value < 0.05 will be considered a significant improvement in the MedExT group.

Three secondary treatment responses will be studied. The first will test whether the MedExT group will significantly increase mean scores on the Freiburg Mindfulness Inventory as determined by a two-sample t-test or the Rank Sum test given distributional properties of the data ($P < 0.05$). The second will explore whether the MedExT treatment will significantly influence a mean change in responses on the three psychological inventories administered; the Fear Avoidance Beliefs Questionnaire, the STAI state anxiety inventory and the STAI state trait inventory, $p < 0.02$. The third outcome measured will study mean response changes in the series of 14 Quantitative Sensory Tests measured at baseline and at the completion of the 4-week intervention period. Significant mean pre/post differences between groups will be identified using the two-sample t-test or the Rank Sum test where appropriate adjusting the significance level to 0.005. Additionally two pain outcome measures will be repeatedly observed throughout the study taken at baseline and on each intervention day. These measures are the VAS pain intensity score and the VAS pain unpleasantness. A repeated measures multivariate analysis of variance (MANOVA) procedure will be used to determine if the vector of timed responses is significantly different between the two study groups.

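### Drawing the QST stimulus order afresh on Day 1 and Day 29 may add avoidable noise, though not bias, to the secondary QST change scores

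*Protocol*

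**What the plan says.** In Protocol section 3, the sensory testing paragraph says that the order of the mechanical, thermal and pressure tests "will be randomized during each day 1 versus day 29 testing". It does not say that a participant keeps one order for both visits, or that the order is recorded. The wording is loose, but a fresh draw at each session is the natural reading.

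The three modalities are tested on the forearm and the low back, some of them with "acute noxious stimuli (painful stimuli) that do not damage tissue". On spacing, the paragraph says: "Time between different tests will be >5 min to allow the subject to rest". For the pressure assay, the repeat trials use separate sites "to avoid damage or sensitization to a single area". Within the heat assay the site sequence is fixed: "forearm then lower back at the site of back pain". For the pressure ratings, "subjects will be tested on day 29 at their original baseline pressure threshold (from day 1) AND the new threshold determined day 29", so Day 29 has one more rated pressure stimulus than Day 1.

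The SAP treats the 14 QST measures as the third secondary response: "Significant mean pre/post differences between groups will be identified", by two-sample t-test or rank sum test at a per-test level of 0.005. The analysis has no term for order or position.

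**The concern.** A change score removes whatever is the same at both visits. If a painful test alters the response to the next one, a test done first on Day 1 and third on Day 29 carries a shift that has nothing to do with treatment. The protocol fixes the order of sites within the heat test, so that part repeats at both visits. The order of the modalities, as written, does not.

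What is at stake is precision in a secondary outcome. The per-test level of 0.005 is strict, so extra variance costs power. Protocol section 8 also intends the trial's estimates to inform the design and power of a larger trial, and an inflated SD of QST change would carry into that planning. The primary outcome, the Roland-Morris score, is not affected.

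**Working it through.** The plan gives no sample size, SD, pre/post correlation or carry-over size for QST, so it has no figure of its own to reproduce.

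**Inputs from the documents.** Three modalities, ordered at random at each of two visits (Protocol section 3); analysis of pre/post differences between groups at 0.005 (SAP).

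**Step 1: how often the order changes.** There are 3! = 6 orders. With independent draws, P(same full order) = 1/6, so P(different) = 5/6 = 83%. For a given test, P(same position) = 1/3, so P(different position) = 2/3 = 67%.

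**Step 2: bias.** Position has the same distribution on both days and in every group. The expected order contribution to the mean change is therefore zero in each group, and zero in the between-group contrast. A t-test simulation (40,000 runs; 10 to 30 per arm; linear carry-over of 0.3 or 0.5 session SD per position) agreed. With re-drawn order, the between-group bias was within about ±0.003 SD and the type I error was 0.0048 to 0.0057 against a nominal 0.005.

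**Step 3: added variance.** Assume a linear position effect of 0, d/2, d for first, second, third, in units of the SD of the change score without order effects.
- Variance per visit: [(d/2)² + 0 + (d/2)²]/3 = d²/6.
- Two independent visits: d²/6 + d²/6 = d²/3.
- Same order on both days, same additive effect on both: 0.

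If instead the whole effect appears after the first test (0, d, d), the variance per visit is d² × (2/3)(1/3) = 2d²/9, and two visits add 4d²/9.

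| Assumed d | Linear: added variance | Interval wider by | Step: added variance | Interval wider by |
|---|---|---|---|---|
| 0 | 0 | 0 | 0 | 0 |
| 0.5 | 0.25/3 = 8% | √1.083 = 1.041, 4% | 0.25 × 4/9 = 11% | √1.111 = 1.054, 5% |
| 1.0 | 1/3 = 33% | √1.333 = 1.155, 15% | 4/9 = 44% | √1.444 = 1.202, 20% |

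**Step 4: what that means for power (illustration only).** Assume 20 per arm, a pre/post correlation of 0.7, a between-group difference in change of 0.8 session SD and a two-sided 0.005 level (the SAP does not state sidedness for QST). The change variance without order effects is 2(1 − 0.7) = 0.6. Let c be the carry-over in session SDs, either as a step (0, c, c) or linear (0, c, 2c).
- c = 0.2: added variance 0.0178 (step) to 0.0533 (linear). The required N rises by 0.0178/0.6 = 3% to 0.0533/0.6 = 9%. Power by normal approximation falls from 67.7% to between 66.0% and 62.7%.
- c = 0.3: added variance 0.04 to 0.12. The required N rises by 7% to 20%. Power falls to between 63.9% and 56.9%.

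The t-test simulation gives lower absolute power at 20 per arm: about 61% with one order kept and 51% with re-drawn order, for linear c = 0.3. The direction is the same.

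**The case against.** The strongest reply is that randomising order at each visit is a valid way to prevent systematic order effects, and that nothing in the documents shows a carry-over large enough to matter. Section 3 describes filament pain as transient. Section 9 says that heat and pressure pain usually ends as soon as the procedure does. More than 5 minutes separates different tests. The one mention of sensitisation concerns repeated pressure on a single spot and is already handled by moving the site; it is not evidence that one modality affects another. All of this stands: d may be small or zero, and then nothing is lost.

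Several stronger readings are tempting but not supported:
- A reader might infer that the group comparison is biased or its error rate inflated. It is not, because order is unrelated to group (step 2).
- A reader might count chance imbalance in order shifts between groups as a separate harm. It is ordinary sampling error that the test's variance already reflects.
- A reader might infer that planned correlations with QST change would be weakened. Section 8 plans correlations between assessments where appropriate but does not mention QST change scores.
- A reader might stress the loss because the trial is small. Neither document states a sample size.

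The remedy also has limits. Even with one order per participant, tests that follow pressure have a different history on Day 29 because of the extra pressure rating. The familiarisation with the stimuli before baseline testing is another difference between the sessions. Sensitisation that treatment itself alters would not cancel under either scheme.

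**Conclusion.** The point holds as a minor matter of precision. As written, order is most naturally drawn afresh at each visit, the SAP analyses change without an order term, and any order effect therefore adds variance to the secondary QST change scores. The 5/6 and 2/3 follow from independent draws alone. The size of the loss is conditional: d²/3 under a linear effect, so about 8% more variance at d = 0.5 and none at d = 0. The documents give no value for d, and the power figures rest further on an assumed sample size, correlation and treatment difference. No analysis is invalidated. The case for acting is that, for a change-score analysis, re-drawing the order on Day 29 has no evident benefit, whereas keeping it costs almost nothing.

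**What to change.** In the sensory testing paragraph of Protocol section 3, state that the order of the three stimuli is randomised once per participant on Day 1, recorded on the QST form and repeated on Day 29. If one order per participant was always intended, the sentence needs only this clarification. The tests themselves do not change.

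Where Day 1 testing has been done without a fixed order, record the order used at each visit and add the test's Day 1 and Day 29 positions as covariates when comparing QST change between groups. The SAP should say so, since this replaces the plain two-sample test for those measures.

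The cost is one protocol sentence and one field on the form. Order says nothing about study group, so the QST examiner's blinding is unaffected. Expect order noise to be reduced rather than removed entirely, for the reasons given in the objection.
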